8.3 ADVERSE EVENTS AND SERIOUS ADVERSE EVENTS

8.3.1 DEFINITION OF ADVERSE EVENTS

This protocol uses the definition of adverse event from 21 CFR 312.32 (a): any untoward medical occurrence associated with the use of an intervention in humans, *whether or not considered intervention-related*.

An adverse event will be defined as any undesirable symptom, accident, or medical condition considered related or possibly related to the intervention. Medical conditions present before the intervention will be considered adverse events only if they worsen after starting the study and that

worsening is considered to be related to the study intervention. An adverse event is also any undesirable and unintended effect of research occurring in human subjects as a result of the collection of identifiable private information under the research.

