7.1 DISCONTINUATION OF STUDY INTERVENTION/EXPERIMENTAL MANIPULATION

When a participant discontinues from Somryst but not from the study, remaining study procedures will be completed as indicated by the study protocol. If a clinically significant finding is identified (including, but not limited to changes from baseline) after enrollment, the investigator or qualified designee will determine if any change in participant management is needed. Any new clinically relevant finding will be reported as an adverse event (AE).

The data to be collected at the time of study intervention discontinuation will include the following:

- The reason(s) for discontinuing the participant from the intervention, and methods for determining the need to discontinue
- If the participant is due to complete assessments within 2 weeks of being discontinued from the study intervention, those assessments will be administered at the time of discontinuation; if the next scheduled assessments are more than 2 weeks from the discontinuation date, the discontinued participant will wait for the next scheduled assessment. Thereafter, the participant will be included in all future scheduled assessments, even though not participating in the intervention.

18 May 2022

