8.3.2 DEFINITION OF SERIOUS ADVERSE EVENTS

Serious adverse event: The adverse event will be deemed serious if it is determined to be associated or possibly associated with study involvement, and results in any of the following outcomes: death, a life-threatening adverse experience, in-subject hospitalization or prolongation of existing hospitalization, a persistent or significant disability/incapacity, or a congenital anomaly/birth defect. Important medical events that may not result in death, be life-threatening, or require hospitalization may be considered a serious adverse experience when, based upon appropriate medical judgment, they may jeopardize the subject and may require medical or surgical intervention to prevent one of the outcomes listed above.

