8.3.3.2 RELATIONSHIP TO STUDY INTERVENTION/EXPERIMENTAL MANIPULATION

All adverse events (AEs) will have their relationship to study procedures, including the intervention, assessed by an appropriately-trained clinician (PI and study physician Co-I) based on temporal relationship and his/her clinical judgment. The degree of certainty about causality will be graded using the categories below.

18 May 2022

- Definitely Related There is clear evidence to suggest a causal relationship, and other possible contributing factors can be ruled out. The clinical event, including an abnormal laboratory test result, occurs in a plausible time relationship to study procedures administration and cannot be explained by concurrent disease or other drugs or chemicals. The response to withdrawal of the study procedures should be clinically plausible. The event must be pharmacologically or phenomenologically definitive.
- Probably Related There is evidence to suggest a causal relationship, and the influence of other factors is unlikely. The clinical event, including an abnormal laboratory test result, occurs within a reasonable time after administration of the study procedures, is unlikely to be attributed to concurrent disease or other drugs or chemicals, and follows a clinically reasonable response on withdrawal.
- Potentially Related There is some evidence to suggest a causal relationship (e.g., the event occurred within a reasonable time after administration of study procedures). However, other factors may have contributed to the event (e.g., the participant's clinical condition, other concomitant events). Although an AE may rate only as "possibly related" soon after discovery, it can be flagged as requiring more information and later be upgraded to "probably related" or "definitely related", as appropriate.
- Unlikely to be related A clinical event, including an abnormal laboratory test result, whose temporal relationship to study procedures administration makes a causal relationship improbable (e.g., the event did not occur within a reasonable time after administration of the study procedures) and in which other drugs or chemicals or underlying disease provides plausible explanations (e.g., the participant's clinical condition, other concomitant treatments).

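### Section 8.3.1 defines an adverse event in two incompatible ways, 8.3.2 makes seriousness depend on relatedness, and 9.4.4 plans no summary of harms by arm

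*Combined protocol and SAP*

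**What the plan says.** All references are to the combined protocol and SAP.

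- **8.3.1, first paragraph.** Adopts a regulatory definition under which an untoward medical occurrence counts "whether or not considered intervention-related". The same sentence ties the occurrence to use of an intervention.
- **8.3.1, second paragraph.** "An adverse event will be defined as any undesirable symptom, accident, or medical condition considered related or possibly related to the intervention". A pre-existing condition counts only if it worsens after the start of the study and that "worsening is considered to be related to the study intervention". A further sentence adds unintended effects on participants "as a result of the collection of identifiable private information under the research".
- **8.3.2, first sentence.** "The adverse event will be deemed serious if it is determined to be associated or possibly associated with study involvement", and it must also lead to one of the listed outcomes, which include death and hospitalization.
- **8.3.2, second sentence.** "Important medical events that may not result in death, be life-threatening, or require hospitalization may be considered a serious adverse experience", subject to medical judgment. The relatedness condition is not repeated here.
- **8.3.3.2.** Grades AEs on five levels of relatedness. The lowest two are unlikely to be related and not related. The assessors are the PI and a study physician.
- **8.3.4.** AEs on study are documented whatever their relationship, and deterioration of a baseline condition is recorded as an AE. Capture is of AEs that the protocol does not otherwise preclude.
- **9.4.4.** Safety analyses are given as N/A.

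**The concern.** Two rules in one section give different answers for the same event, and no passage says which governs. What reaches the database then depends on which paragraph a staff member applies.

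The related-only rule is the more harmful of the two for a randomized comparison. In the Somryst arm, relatedness to the intervention is a meaningful question. In the minimally enhanced usual care (mEUC) arm, patients receive a brochure and their ordinary care, and it is unclear what the intervention would be. The same road accident could count in one arm and not in the other. Section 6.3 leaves the PI unblinded, so the filter would be applied with knowledge of the arm.

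This matters because the protocol names a specific risk. Sections 2.3.1 and 2.3.3 describe tiredness from sleep restriction, and 8.3.3.3 lists motor vehicle and work accidents linked to fatigue as potentially intervention-related serious events. With no safety analysis planned, nothing commits the trial to reporting those events by arm.

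**Working it through.** **Step 1. An event judged unrelated, rule by rule.**

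| Place | Is it an AE? |
|---|---|
| 8.3.1, first paragraph | Yes |
| 8.3.1, second paragraph | No |
| 8.3.3.2, two lowest grades | Presupposes yes |
| 8.3.4, documentation rule | Presupposes yes, unless the carve-out for precluded AEs is read as deferring to 8.3.1 |

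**Step 2. A prior condition that worsens for reasons judged unrelated.** Under the second paragraph of 8.3.1 it is not an AE. Under 8.3.4 it is recorded as one.

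**Step 3. Section 7.1.** It says that new clinically relevant findings are reported as AEs, with no relatedness condition. It sits under discontinuation of the intervention and opens with participants who stop Somryst. It is limited support for a broad rule and does not clearly reach mEUC patients.

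**Step 4. A death or hospitalization judged unrelated.** The first sentence of 8.3.2 excludes it from serious adverse events (SAEs). The second does not bring it back, because that sentence covers important medical events that may not involve death or hospitalization. The consequences are:

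- 8.3.6 (report within 10 working days) is not triggered.
- Immediate reporting under 8.3.5, and unanticipated-problem status under 8.4.1 with its 24-hour route in 8.4.2, each require relatedness, so neither applies.
- If it is an AE (first paragraph of 8.3.1), it is reported at continuing renewal under 8.3.5. Under the second paragraph it may not be an AE at all.

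**Step 5. Precision of a by-arm table.** The plan states no harms figure to reproduce. Inputs from 9.2: 200 randomized 1:1, so 100 per arm; 15% attrition leaves 200 × 0.85 = 170, or 85 per arm if attrition is equal (assumed). Event rates are assumed at about 2%, 5% and 10%.

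Wilson limits for x events in n, with p = x/n and z = 1.96:

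l, u = [p + z²/(2n) ± z·√(p(1−p)/n + z²/(4n²))] / (1 + z²/n)

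With the same x in both arms, the Newcombe 95% interval for the risk difference is ±√[(p−l)² + (u−p)²].

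Example, n = 100 and x = 2: l = 0.55%, u = 7.00%, so √(1.45² + 5.00²) = 5.21 points.

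| n per arm | Events in each arm | 95% half-width (points) |
|---|---|---|
| 100 | 2 | 5.21 |
| 100 | 5 | 6.80 |
| 100 | 10 | 8.68 |
| 85 | 2 | 6.07 |
| 85 | 4 | 7.36 |
| 85 | 9 | 9.67 |

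The counts at 85 are 1.7, 4.25 and 8.5 rounded to whole events.

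Power for 5% against 10% at two-sided 0.05, by Fisher's exact test with full enumeration, is 0.190 at 100 per arm and 0.157 at 85. The normal approximation with pooled null variance gives 0.267 and 0.234. By either method the table is descriptive and not a test.

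**The case against.** The strongest reply is that harms are less neglected than N/A suggests. Epworth sleepiness is a secondary endpoint compared by arm and bears on the main expected harm. Section 9.4.9 tests group differences in sleep-medication use. Table 1 has a hospitalization row that appears to be marked at post-treatment and 6 months (the table is broken in the text), and 6.1.1 puts both arms on the same assessment schedule. Section 9.4.3 collects emergency visits and hospitalizations in both arms, 9.4.8 lists individual data, and 8.2 has a DSMB review AEs. The protocol describes the study as low risk. All of this stands and lowers the urgency. None of it is a summary of AEs or SAEs by arm, and none of it reconciles the two definitions.

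It can also be said that 8.3.4 settles the matter by requiring documentation whatever the relationship. But it applies to AEs, the term that 8.3.1 defines twice, and its carve-out can be read as deferring to the narrower definition.

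A third reply is that the condition in 8.3.2 is a choice and contradicts no other passage. That is fair: it is a weakness of definition, not an inconsistency. The argument about comparability between arms also does not carry over to it, because 8.3.2 refers to study involvement and mEUC patients complete the same assessments.

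A reader might infer that unrelated events will go uncollected or that AE counts will be biased. The documents do not support that. Section 8.3.4 points towards full capture, and 6.3 blinds the staff who do the 9-week and 6-month assessments, where 8.2 places the AE interviews. The problem arises only if the related-only wording is the one applied.

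**Conclusion.** The point holds and should be fixed. Section 8.3.1 contradicts itself, and its second paragraph conflicts with 8.3.4 and with the grades in 8.3.3.2. The first sentence of 8.3.2 takes deaths and hospitalizations judged unrelated out of the SAE category and so out of 8.3.6. No AE or SAE summary by arm is planned anywhere in the document.

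The size of any imbalance cannot be derived, because there are no event rates and no way to know which rule staff would follow. The intervals above describe the proposed table under assumed rates, not the size of the defect. The conclusion rests on the text alone. It does not touch the sample size or the primary ISI analysis, and nothing here suggests that the efficacy result would be biased.

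**What to change.** 1. **8.3.1.** Remove the relatedness conditions on AEs and on worsening, so that the section agrees with 8.3.4. State that, after randomization, an AE is any untoward medical occurrence in a participant in either arm. Deleting the second paragraph's conditions is not enough, because the first paragraph's link to use of an intervention could still be read as excluding mEUC. Keep the sentence on identifiable private information.
2. **8.3.2.** Define seriousness by outcome and record relatedness separately under 8.3.3.2. Then reconcile 8.3.5, 8.3.6 and 8.4.2 with that definition and with local policy, so that the definition alone does not set the reporting clock. The threshold is for the sponsor and the IRB to set.
3. **9.4.4.** Replace N/A with a descriptive table by randomized arm of participants with any AE, any SAE, and any motor vehicle or work-related accident, with onset after randomization. Count all such accidents, without requiring attribution to fatigue. Give risk differences with 95% confidence intervals and the numbers interviewed at 9 weeks and 6 months, and note the limited precision.

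The cost is wording in these sections, more event forms, possibly more SAE evaluations and reports, and one table. No visits are added.

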8.3.2 DEFINITION OF SERIOUS ADVERSE EVENTS

Serious adverse event: The adverse event will be deemed serious if it is determined to be associated or possibly associated with study involvement, and results in any of the following outcomes: death, a life-threatening adverse experience, in-subject hospitalization or prolongation of existing hospitalization, a persistent or significant disability/incapacity, or a congenital anomaly/birth defect. Important medical events that may not result in death, be life-threatening, or require hospitalization may be considered a serious adverse experience when, based upon appropriate medical judgment, they may jeopardize the subject and may require medical or surgical intervention to prevent one of the outcomes listed above.

8.3.3 CLASSIFICATION OF AN ADVERSE EVENT

8.3.3.1 SEVERITY OF EVENT

For adverse events (AEs) not included in the protocol defined grading system, the following guidelines will be used to describe severity.

- No adverse event or within normal limits
- **Mild** Events require minimal or no treatment and do not interfere with the participant's daily activities.
- **Moderate** Events result in a low level of inconvenience or concern with the therapeutic measures. Moderate events may cause some interference with functioning.
- Severe Events interrupt a participant's usual daily activity and may require systemic drug therapy or other treatment. Severe events are usually potentially life-threatening or incapacitating. Of note, the term "severe" does not necessarily equate to "serious".
- Life-threatening or disabling adverse event
- Fatal adverse event

8.3.3.2 RELATIONSHIP TO STUDY INTERVENTION/EXPERIMENTAL MANIPULATION

All adverse events (AEs) will have their relationship to study procedures, including the intervention, assessed by an appropriately-trained clinician (PI and study physician Co-I) based on temporal relationship and his/her clinical judgment. The degree of certainty about causality will be graded using the categories below.

18 May 2022

- Definitely Related There is clear evidence to suggest a causal relationship, and other possible contributing factors can be ruled out. The clinical event, including an abnormal laboratory test result, occurs in a plausible time relationship to study procedures administration and cannot be explained by concurrent disease or other drugs or chemicals. The response to withdrawal of the study procedures should be clinically plausible. The event must be pharmacologically or phenomenologically definitive.
- Probably Related There is evidence to suggest a causal relationship, and the influence of other factors is unlikely. The clinical event, including an abnormal laboratory test result, occurs within a reasonable time after administration of the study procedures, is unlikely to be attributed to concurrent disease or other drugs or chemicals, and follows a clinically reasonable response on withdrawal.
- Potentially Related There is some evidence to suggest a causal relationship (e.g., the event occurred within a reasonable time after administration of study procedures). However, other factors may have contributed to the event (e.g., the participant's clinical condition, other concomitant events). Although an AE may rate only as "possibly related" soon after discovery, it can be flagged as requiring more information and later be upgraded to "probably related" or "definitely related", as appropriate.
- Unlikely to be related A clinical event, including an abnormal laboratory test result, whose temporal relationship to study procedures administration makes a causal relationship improbable (e.g., the event did not occur within a reasonable time after administration of the study procedures) and in which other drugs or chemicals or underlying disease provides plausible explanations (e.g., the participant's clinical condition, other concomitant treatments).
- Not Related The AE is completely independent of study procedures administration, and/or evidence exists that the event is definitely related to another etiology. There must be an alternative, definitive etiology documented by the clinician.]

8.3.3.3 EXPECTEDNESS

A clinician (general internist) with appropriate expertise in insomnia will be responsible for determining whether an adverse event (AE) is expected or unexpected. An AE will be considered unexpected if the nature, severity, or frequency of the event is not consistent with the risk information previously described for the study procedures.

Anticipated or expected adverse events will include: initial discomfort/embarrassment from discussion of topics of a sensitive nature or wearing the actigraph, initial tiredness/fatigue from the sleep restriction component of the intervention, and participant confidentiality and privacy concerns about sharing personal information on a digital platform.

Potentially intervention related serious adverse events will include fatigue-related accidents (motor vehicle accidents, work-related accidents).

18 May 2022

8.3.4 TIME PERIOD AND FREQUENCY FOR EVENT ASSESSMENT AND FOLLOW-UP

The occurrence of an adverse event (AE) or serious adverse event (SAE) may come to the attention of study personnel during study visits and interviews of a study participant presenting for medical care, or upon review by a study monitor.

All AEs, not otherwise precluded per the protocol, will be captured on the appropriate case report form (CRF). Information to be collected includes event description, time of onset, clinician's assessment of severity, relationship to study procedures (assessed only by those with the training and authority to make a diagnosis), and time of resolution/stabilization of the event. All AEs occurring while on study will be documented appropriately regardless of relationship. All AEs will be followed to adequate resolution.

Any medical or psychiatric condition that is present at the time that the participant is screened will be considered as baseline and not reported as an AE. However, if the study participant's condition deteriorates at any time during the study, it will be recorded as an AE.

Changes in the severity of an AE will be documented to allow an assessment of the duration of the event at each level of severity to be performed. Documentation of onset and duration of each episode will be maintained for AEs characterized as intermittent.

Research Staff will record events with start dates occurring any time after informed consent is obtained until 7 (for non-serious AEs) or 30 days (for SAEs) after the last day of study participation. At each study visit, the investigator will inquire about the occurrence of AE/SAEs since the last visit. Events will be followed for outcome information until resolution or stabilization.

8.3.5 ADVERSE EVENT REPORTING

Any adverse event (AE) or unanticipated problem will be identified, responded to, recorded by the PI. If the AE or problem is unexpected, related to study involvement, and puts the participant at increased risk, it will be reported to the Columbia IRB immediately, in accordance with local policies, in addition to the Data Safety and Monitoring Board (DSMB) and if necessary, AHRQ. All other AEs and problems will be reported at the time of continuing renewal.

8.3.6 SERIOUS ADVERSE EVENT REPORTING

In consultation with the PI, a trained member of the study team (study physicians, [name], [name]) will be responsible for conducting an evaluation of a serious adverse event and shall report the results of such

18 May 2022

evaluation to the NIH and the reviewing Institutional Review Board (IRB) as soon as possible, but in no event later than 10 working days after the investigator first learns of the event

8.3.7 REPORTING EVENTS TO PARTICIPANTS

The PI and study team will follow DSMB guidance regarding reporting of adverse events to participants.

8.3.8 EVENTS OF SPECIAL INTEREST N/A

8.3.9 REPORTING OF PREGNANCY

Pregnancy is not reported as an adverse event. In the event of a pregnancy during trial participant, participants will be asked to discontinue the study intervention.

8.4 UNANTICIPATED PROBLEMS

8.4.1 DEFINITION OF UNANTICIPATED PROBLEMS

This protocol uses the definition of Unanticipated Problems as defined by the Office for Human Research Protections (OHRP). OHRP considers unanticipated problems involving risks to participants or others to include, in general, any incident, experience, or outcome that meets all of the following criteria:

- Unexpected in terms of nature, severity, or frequency given (a) the research procedures that are described in the protocol-related documents, such as the Institutional Review Board (IRB)approved research protocol and informed consent document; and (b) the characteristics of the participant population being studied;
- Related or possibly related to participation in the research ("possibly related" means there is a reasonable possibility that the incident, experience, or outcome may have been caused by the procedures involved in the research); and
- Suggests that the research places participants or others at a greater risk of harm (including physical, psychological, economic, or social harm) than was previously known or recognized.

8.4.2 UNANTICIPATED PROBLEMS REPORTING

18 May 2022

The investigator will report unanticipated problems (UPs) to the reviewing Institutional Review Board (IRB) and to the Data Safety and Monitoring Board/AHRQ. The UP report will include the following information:

- Protocol identifying information: protocol title and number, PI's name, and the IRB project number
- A detailed description of the event, incident, experience, or outcome
- An explanation of the basis for determining that the event, incident, experience, or outcome represents an UP
- A description of any changes to the protocol or other corrective actions that have been taken or are proposed in response to the UP

To satisfy the requirement for prompt reporting, UPs will be reported using the following timeline:

- UPs that are serious adverse events (SAEs) will be reported to the IRB and to the Data Safety and Monitoring Board/AHRQ immediately within 24 hours of the investigator becoming aware of the event
- Any other UP will be reported to the IRB and to the DCC/study sponsor/funding agency within 14 days of the investigator becoming aware of the problem
- All UPs should be reported to appropriate institutional officials (as required by an institution's written reporting procedures), the supporting agency head (or designee), and the Office for Human Research Protections (OHRP) within 30 days of the IRB's receipt of the report of the problem from the investigator

These policies are informed by *https://www.nhlbi.nih.gov/grants-and-training/policies-and-guidelines/nhlbi-adverse-event-and-unanticipated-problem-reporting-policy.*

